**Details:**

The difference in proportions is produced in Step 1.

The confidence intervals for the estimated difference in proportions are produced using the cumulative distribution function method of Reeve.

For completeness, the 95% and 90% CI for risk difference will also be calculated for ACR20.

The SAS code to implement the method is provided next page and require as input:

1. Variance (g) is directly provided by SAS PROC GENMOD Empirical Standard Error Estimates.
2.  $Cov(b_i, b_j)$  and  $Cov(\gamma, b_i) \forall i, j \in [0; k]$  are directly provided by SAS PROC GENMOD Covariance Matrix (Empirical).
3. Variance (z) will be calculated using the formula:

$$Var(z) = Var\left(b_0 + b_1x_1^* + \dots + b_kx_k^*\right) = \sum_{i,j=0}^k x_i^* x_j^* Cov(b_i, b_j) \text{ where } x_0^* = 1$$

4. Covariance (g,z) will be calculated using the formula:

$$Cov(g, z) = Cov\left(\gamma, b_0 + b_1x_1^* + \dots + b_kx_k^*\right) = \sum_{i=0}^k x_i^* Cov(\gamma, b_i)$$

Then VarTheta is equal to  $\begin{pmatrix} Var(g) & Cov(g, z) \\ Cov(g, z) & Var(z) \end{pmatrix}$

Reference: Reeve R. Confidence interval of difference of proportions in logistic regression in presence of covariates. Statistical Methods in Medical Research. 2016. DOI : 10.1177/0962280216631583

## SAS CODE FOR DIFFERENCE IN PROPORTION CIs

```
%macro m_prop_diff(trtn = , outn = );

  ****Get difference and SE CI;
  ods output RiskDiffColl = _riskdiff PdiffCLs = _diffcl;

  proc freq data = adefl1;
    where &trtn.n in (&trtn.);
    by paramcd param paramn avisitn avisit;
    table &trtn.n * aval / riskdiff(column = 1 cl = wilson equal var =
sample);
  run;

  data diff1_&outn.;
    set _riskdiff(in = a where = (strip(lowercase(row)) = "difference"))
      _diffcl(in = b);
    by paramcd param paramn avisitn avisit;
    length col4 $200;
    if a then do;
      seq = 3;
      if not missing(risk) and not missing(ase) then col4 = strip(put(risk
* 100, 8.1)) || " (" || strip(put(ase * 100, 8.2)) || ")";
      if compress(scan(col4, 1, "(")) = "-0.0" then col4 = tranwrd(col4, "-",
", ");
    end;
    if b then do;
```

Document: \\ieedc-vnasc01\Biosdata\Archigen\SAIT101\YWA21301\Biostatistics\Documentation\SAP	Version Number: V2.0	
Author:	Version Date:	13Feb2019

Template No: CS_TP_BS016 Revision 4	Reference: CS_WI_BS005
Effective Date: 01Apr2016	

```
seq = 4;
if not missing(lowercl) and not missing(uppercl) then col4 =
"(|strip(put(lowercl * 100, 8.2))||", "||strip(put(uppercl * 100, 8.2))||");
end;
subseq = &outn.;
run;

****Get adjusted difference and SE;
ods output LSMeans = _lsmean parameterestimates = est covb = covb diffs =
diff;

proc genmod data = adefl1;
where &trtn in (&trtn.);
by paramcd param paramn avisitn avisit;
class &trtn / param = GLM ref = last;
model aval(event = '1') = &trtn das28c_b / dist = binomial link = logit
covb;
lsmeans &trtn / ilink cl diff = all obsmargins;
run;

data diff2_&outn.;
set _lsmean;
by paramcd param paramn avisitn avisit;
length col4 $200;
mu_lag = lag(mu);
if first.avisit then mu_lag = .;
else if last.avisit then do;
diff = mu_lag - mu;
col4 = put(diff * 100, 8.1);
if compress(col4) = "-0.0" then col4 = tranwrd(col4, "-", "");
output;
end;
run;

/*macro mtest;*/
****CI;
**Get param info;
proc sql noprint;
select count(distinct paramn) into : paramnum from adefl1;
select distinct paramn into : par1 - : par%sysfunc(compress(¶mnum.))
from adefl1;
quit;

**Get visit info;
proc sql noprint;
select count(distinct avisitn) into : vsnum from adefl1;
select distinct avisitn into : vs1 - : vs%sysfunc(compress(&vsnum.)) from
adefl1;
quit;

**Do loop for all visits;
%do j = 1 %to &vsnum.;

proc sql noprint;
select count(*) into : obsnum from diff
where avisitn = &&vs&j.. and int(probz) ne 1
;
select count(*) into : obsnum2 from est
```

Document: \\eedc-vnasc01\Biosdata\Archigen\SAIT101\YWA21301\Biostatistics\Documentation\SAP

Author:

Version Number:

V2.0

Version Date:

13Feb2019

Template No: CS\_TP\_BS016 Revision 4  
Effective Date: 01Apr2016

Reference: CS\_WI\_BS005

```
        where avisitn = &&vs&j.. and strip(level1) = "1" and not  
missing(probchisq) and round(probchisq, 0.001) < 1  
    ;  
quit;  
%put &obsnum. &obsnum2.;
```

```
%if &obsnum2. > 0 %then %do;
```

```
    data covb1;  
        set covb;  
        where avisitn = &&vs&j..;  
run;
```

```
    data est1;  
        set est;  
        where avisitn = &&vs&j..;  
run;
```

```
proc sql noprint;  
    create table listx as  
        select 1 as mx0, mean(das28c_b) as mx1, paramn  
        from adefl1  
        where &trtn in (&trtn.) and avisitn = &&vs&j..  
        group by paramn  
    ;  
quit;
```

```
proc transpose data = listx out = listx_t(drop = _name_);  
    by paramn;  
    var mx0 mx1;  
run;
```

```
data covbx;  
    set covb1;  
    if rowname = "Prm2" then delete;  
    drop prm2 rowname paramcd param avisit;  
run;
```

```
**Do loop for each param;  
%do i = 1 %to ¶mnum.;
```

```
    proc sql noprint;  
        select count(*) into: num from covbx  
        where paramn = &&par&i..;  
    quit;
```

```
    data Plistx;  
        set listx;  
        where paramn = &&par&i..;  
        drop paramn;  
run;
```

```
    data Pcovbx;  
        set covbx;  
        where paramn = &&par&i..;  
        drop paramn avisitn;  
run;
```

Document: \\eedc-vnasc01\Biosdata\Archigen\SAIT101\YWA21301\Biostatistics\Documentation\SAP  
Author:

Version Number: V2.0  
Version Date: 13Feb2019

Template No: CS\_TP\_BS016 Revision 4  
Effective Date: 01Apr2016

Reference: CS\_WI\_BS005

```
data Pcovb1;  
    set covb1;  
    where paramn = &&par&i..;  
    drop paramn avisitn;  
run;
```

```
data Plistx_t;  
    set listx_t;  
    where paramn = &&par&i..;  
    drop paramn;  
run;
```

```
proc fcmp;  
    array mat1[1,&num.]/nosymbols;  
    rc=read_array('Plistx',mat1);  
  
    array mat2[&num.,&num.]/nosymbols;  
    rc=read_array('Pcovbx',mat2);  
  
    array mat3[&num.,1]/nosymbols;  
    rc=read_array('Plistx_t',mat3);  
  
    array res1[1,&num.];  
    call mult(mat1,mat2,res1);  
  
    array result[1,1];  
    call mult(res1,mat3,result);  
  
    rc= write_array('varZ',result);  
quit;
```

```
proc sql noprint;  
    select put(result1,best12.) into: varz from varz;  
quit;
```

```
%put Varz is: &varz.;
```

```
data cov_g;  
    set Pcovb1;  
    keep prm2;  
    if rowname="Prm2" then delete;  
run;
```

```
proc fcmp;  
    array mat1[1,&num.]/nosymbols;  
    rc=read_array('Plistx',mat1);  
  
    array mat2[&num.,1]/nosymbols;  
    rc=read_array('cov_g',mat2);  
  
    array mat3[1,1];  
    call mult(mat1,mat2,mat3);  
    rc=write_array('covGZ',mat3);  
quit;
```

Document: \\eedc-vnasc01\Biosdata\Archigen\SAIT101\YWA21301\Biostatistics\Documentation\SAP  
Author:

Version Number: V2.0  
Version Date: 13Feb2019

Template No: CS\_TP\_BS016 Revision 4  
Effective Date: 01Apr2016

Reference: CS\_WI\_BS005

```
proc sql noprint;  
    select put(mat31,best12.) into: covgz from covgz;  
    select put(prm2, best12.) into: varg from Pcovb1 where  
rowname="Prm2";  
quit;
```

```
proc fcmp;  
    array varcov[2,2] (&varg.,&covgz.,&covgz., &varz.);  
    rc=write_array('varcov',varcov);  
    put varcov=;  
quit;
```

```
data prod_z;  
    set est1;  
    where paramn = &&par&i..;  
    length newvar $20;  
    newvar=strip(parameter)||strip(level1);  
run;
```

```
proc transpose data=prod_z out=prodz_t;  
    var estimate;  
    id newvar;  
run;
```

```
data prodz_t;  
    set prodz_t;  
    X0=intercept;  
    X1=das28c_b;  
    keep x;;  
run;
```

```
proc fcmp;  
    array mat1[1,&num.]/nosymbols;  
    rc=read_array('prodz_t',mat1);  
    array mat3[&num.,1]/nosymbols;  
    rc=read_array('Plistx_t',mat3);  
    array zres[1,1];  
    call mult(mat1,mat3,zres);  
    rc=write_array('zres',zres);  
run;
```

```
proc sql noprint;  
    select put(estimate,best12.) into: g from est1 where  
level1="1" and paramn=&&par&i..;  
    select put(zres1, best12.) into: z from zres;  
quit;
```

```
%put estimate of g and z : &g. &z. ;
```

```
%let K=1000000;  
%let alpha=0.05;
```

```
proc IML;  
    theta={&G. &Z.}; print theta;  
    vartheta={&VARG. &COVGZ. , &COVGZ. &VARZ.}; print  
vartheta;  
    Xc = t(root(Vartheta));
```

Document: \\eedc-vnasc01\Biosdata\Archigen\SAIT101\YWA21301\Biostatistics\Documentation\SAP  
Author: Version Number: V2.0

Version Date: 13Feb2019

Template No: CS\_TP\_BS016 Revision 4  
Effective Date: 01Apr2016

Reference: CS\_WI\_BS005

```
call randseed(456);  
X = j(&K.,2);  
call randgen(X,"Normal");  
X1=X[,1];  
X2=X[,2];  
create X var{X1 X2}; append;  
close X;  
Y=X*Xc;  
G=Y[,1]+Theta[1,1];  
Z=Y[,2]+Theta[1,2];  
DELTA=(1/(1+exp(-(G+Z))))-(1/(1+exp(-Z)));  
call sort(DELTA);  
LOW=DELTA[round(&k.*(&alpha./2))]; print low;  
UP=DELTA[&K.-round(&k.*(&alpha./2))]; print up;  
create uplow var{low up};append;  
quit;
```

```
proc sql noprint;  
select count(*) into : ulobsnum from uplow;  
quit;
```

```
%if &ulobsnum. > 0 %then %do;  
data uplow&j._&i.;  
set uplow;  
paramn = &&par&i..;  
avisitn = &&vs&j..;  
run;  
%end;  
%else %do;  
data uplow&j._&i.;  
paramn = &&par&i..;  
avisitn = &&vs&j..;  
low = .;  
up = .;  
output;  
run;  
%end;
```

```
%end;
```

```
%end;
```

```
%else %do i = 1 %to ¶mnum.;
```

```
data uplow&j._&i.;  
paramn = &&par&i..;  
avisitn = &&vs&j..;  
low = .;  
up = .;  
output;  
run;
```

```
%end;
```

```
%end;
```

```
data diffci_&outn.;
```

Document: \\ieedc-vnasc01\Biosdata\Archigen\SAIT101\YWA21301\Biostatistics\Documentation\SAP  
Author:

Version Number:

V2.0

Version Date:

13Feb2019

Template No: CS\_TP\_BS016 Revision 4  
Effective Date: 01Apr2016

Reference: CS\_WI\_BS005

```
set %do i = 1 %to &vsnum.;
    %do j = 1 %to ¶mnum.;
        uplow&i._&j.
    %end;
%end;
;
length col4 $200;
if not missing(low) and not missing(up) then col4 = "("||strip(put(low *
100, 8.2))||", "||strip(put(up * 100, 8.2))||")";
run;
/*%mend; %mtest;*/
proc datasets library=work memtype=data nolist;
delete uplow varcov zres prodz_t varcov varz plistx pcvbvx pcvb1
plistx_t cov_g covgz varcov
%do i = 1 %to &vsnum.;
    %do j = 1 %to ¶mnum.;
        uplow&i._&j.
    %end;
%end;
;
quit;
```

```
**Set all together;
data stat_f;
set diff1_&outn. (in = a)
diff2_&outn. (in = b)
diffci_&outn. (in = c);
if b then seq = 5;
if c then seq = 6;
if missing(subseq) then subseq = &outn.;
run;
```

```
proc sort data = stat_f;
by paramn avisitn subseq seq;
run;
```

```
data dummy;
%do i = 1 %to ¶mnum.;
    %do j = 1 %to &vsnum.;
        paramn = &&par&i..;
        avisitn = &&vs&j..;
        subseq = &outn.;
        do seq = 3 to 6;
            output;
        end;
    %end;
%end;
run;
```

```
data stat&outn.;
merge dummy(in = a)
stat_f;
by paramn avisitn subseq seq;
if a;
if missing(col4) then do;
if seq in (3 5) then col4 = "- (-)";
else col4 = "(-, -)";
```

Document: \\ieedc-vnasc01\Biosdata\Archigen\SAIT101\YWA21301\Biostatistics\Documentation\SAP  
Author:

Version Number: V2.0  
Version Date: 13Feb2019

Template No: CS\_TP\_BS016 Revision 4  
Effective Date: 01Apr2016

Reference: CS\_WI\_BS005

```
end;  
/* else if seq in (4 6) and missing(col4) then col4 = "(- , -)";*/  
run;  
  
%mend m_prop_diff;
```

---

Document:	\\eedc-vnasc01\Biosdata\Archigen\SAIT101\YWA21301\Biostatistics\Documentation\SAP	Version Number:	V2.0
Author:		Version Date:	13Feb2019

Template No: CS\_TP\_BS016 Revision 4  
Effective Date: 01Apr2016

Reference: CS\_WI\_BS005

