## 15.2. OTHER EFFICACY

### 15.2.1. SECONDARY EFFICACY VARIABLE(S) & DERIVATION(S)

#### Change from Baseline in DAS28-CRP at Week 8, 16, 36, and 52

Change from baseline in DAS28-CRP at week 8, 16, 36 and 52 will be derived with the similar criteria in Section 15.1.1 of this analysis plan.

#### ACR20 response rates at Week 8, 16, 24, 36, and 52

ACR20 response is defined as at least a 20% improvement from baseline if meet the criteria below. A subject will be classified as having achieved an ACR20 response (ACR20 = 1) if the following 3 conditions are satisfied.

$$\frac{\text{Swollen Joint Count at visit } X - \text{Swollen Joint Count at baseline}}{\text{Swollen Joint Count at baseline}} \leq -0.2 \text{ and}$$

$$\frac{\text{Tender Joint Count at visit } X - \text{Tender Joint Count at baseline}}{\text{Tender Joint Count at baseline}} \leq -0.2 \text{ and}$$

At least 3 of following conditions are satisfied.

- $\frac{\text{Patient's Pain at visit } X - \text{Patient's Pain at baseline}}{\text{Patient's Pain at baseline}} \leq -0.2$
- $\frac{\text{Patient's Global at visit } X - \text{Patient's Global at baseline}}{\text{Patient's Global at baseline}} \leq -0.2$
- $\frac{\text{Physician Global at visit } X - \text{Physician Global at baseline}}{\text{Physician Global at baseline}} \leq -0.2$
- $\frac{\text{HAQ-DI at visit } X - \text{HAQ-DI at baseline}}{\text{HAQ-DI at baseline}} \leq -0.2$
- $\frac{\text{CRP at visit } X - \text{CRP at baseline}}{\text{CRP at baseline}} \leq -0.2$

#### ACR50 response rates at Weeks 8, 16, 24, 36, and 52

ACR50 response is defined as at least a 50% improvement from baseline if meet the criteria mentioned in ACR20 above with using 0.5 instead of 0.2.

#### ACR70 response rates at Week 8, 16, 24, 36, and 52

ACR70 response is defined as at least a 70% improvement from baseline if meet the criteria mentioned in ACR20 above with using 0.7 instead of 0.2.

#### Individual components of the ACR improvement criteria on Day 1 and at Week 8, 16, 24, 36, and 52

- Swollen and tender joint count (66/68)
- Patient's assessment of pain
- Physician's global assessment of disease activity
- Patient's global assessment of disease activity
- Patient's assessment of disability (HAQ-DI)
- C-reactive protein level.

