## APPENDIX 4. DETAIL OF MULTIPLE IMPUTATION FOR MISSING AT RANDOM

```
proc mi data = formi2 nimpute = 100 seed = 12345 out = bocfmil minimum = 0;  
  by trt01pn trt01p;  
  var param1_1 param2_1 param3_1  
      param1_2 param2_2 param3_2  
      param1_3 param2_3 param3_3  
      param1_4 param2_4 param3_4;  
  mcmc chain = multiple impute = monotone;  
run;
```

```
proc sort data = bocfmil;  
  by _imputation_ trt01pn usubjid;  
run;
```

```
proc mi data = bocfmil out = bocfmi2 nimpute = 1 seed = 12345 minimum = 0;  
  by _imputation_;  
  var trt01pn param1_1 param2_1 param3_1  
      param1_2 param2_2 param3_2  
      param1_3 param2_3 param3_3  
      param1_4 param2_4 param3_4;  
  monotone regression;  
run;
```

```
****Get LS means and CI;  
%macro m_ancova_mi(trtn = , outn = , avar = );
```

```
ods output SolutionF = _pval_mi Diffs = _lsmeand_mi LSMeans = _lsmean_mi;
```

```
proc mixed data = ADBOCFMI;  
  by _imputation_;  
  where &trtn in (&trtn.);  
  class &trtn;  
  model &avar. = &trtn avalb / solution;  
  lsmeans &trtn / cl pdiff ;  
run;
```

```
proc mianalyze parms(classvar = full) = _lsmean_mi;  
  class &trtn;  
  modeleffects &trtn;  
  ods output parameterestimates = lsmean_&outn.;  
run;
```

```
proc mianalyze parms(classvar = full) = _lsmeand_mi;  
  class &trtn;  
  modeleffects &trtn;  
  ods output parameterestimates = lsmeand_&outn.;  
run;
```

```
proc mianalyze parms = _pval_mi;  
  class &trtn;  
  modeleffects &trtn avalb;  
  ods output parameterestimates = pval_&outn.;  
run;
```

Document: \\eedc-vnasc01\Biosdata\Archigen\SAIT101\YWA21301\Biostatistics\Documentation\SAP  
Author:

Version Number: V2.0  
Version Date: 13Feb2019

Template No: CS\_TP\_BS016 Revision 4  
Effective Date: 01Apr2016

Reference: CS\_WI\_BS005

```
%mend m_ancova_mi;
```

```
****<AVAL>;
```

```
****<SAIT101 vs MabThera>;
```

```
%m_ancova_mi(trtn = 1 2, outn = 1, avar = aval);
```

---

Document: \\ieedc-vnasc01\Biosdata\Archigen\SAIT101\YWA21301\Biostatistics\Documentation\SAP

Author:

Version Number:

V2.0

Version Date:

13Feb2019

Template No: CS\_TP\_BS016 Revision 4  
Effective Date: 01Apr2016

Reference: CS\_WI\_BS005

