**Details:**

The statistical model for the analysis of the ACR20 will be:

$$(M2) \text{ Logit } (E\{\text{ACR20}\}) = \text{treatment} + \text{baseline DAS28-CRP}$$

The following SAS code will be used:

```
PROC GENMOD DATA= ACR20_central;
CLASS TRT;
MODEL response (event='Y') = TRT base-DAS28-CRP / dist=bin link=logit;
lsmeans TRT / ilink;
run;
```

The population adjusted natural scaled proportion are the estimates produced by the LSMEANS statement.

Step 2: Calculation of confidence intervals based on cumulative distribution function method of Reeve

The respective risk-difference confidences intervals are calculated using the risk difference (calculated in Step 1) and the cumulative distribution function method of Reeve with 1,00 simulations.

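### SAP Appendix 5 code takes the unadjusted response difference from the lowest-coded column, which is non-response if the outcome is coded 0/1, and leaves one exploratory treatment pair without an adjusted CI

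*SAP*

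**What the plan says.** SAP 15.2.3 analyses the categorical efficacy variables (ACR20/50/70, major clinical response, remission, EULAR response) with Wilson score 95% CIs and with logistic regression adjusted for baseline DAS28. SAP 15.2.5 asks for the same comparisons for SAIT101 vs Rituxan and MabThera vs Rituxan, as exploratory analyses. Appendix 5 supplies the SAS code meant to implement this.

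- **Unadjusted rows:** PROC FREQ on the table of treatment by `aval`, with "riskdiff(column = 1 cl = wilson equal var" and no ORDER= option.
- **Adjusted rows:** PROC GENMOD with "model aval(event = '1') = &trtn das28c_b / dist = binomial link = logit". The printed difference is the first treatment level minus the second, on the predicted probability of the event.
- **Display:** both go into one output, unadjusted as items 3 and 4, adjusted as items 5 and 6. No printed step changes or labels a sign.
- **Responder code:** SAP 15.2.1 says "A subject will be classified as having achieved an ACR20 response (ACR20 = 1"). No code for non-response is given.
- **Adjusted CI:** it is computed only if the parameter-estimate table holds a row whose `level1` equals 1. The treatment effect g is read from that same row. Otherwise both limits are set to missing and (-, -) is printed.
- **Treatment codes:** Appendix 5 shows none and no macro call. The Appendix 4 call labelled SAIT101 vs MabThera is "m_ancova_mi(trtn = 1 2, outn = 1, avar = aval".

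**The concern.** PROC FREQ orders columns by internal value unless told otherwise, so column 1 is the lowest value of `aval`. If that value is 0, the unadjusted estimate and its CI are for failure to respond, beside an adjusted estimate for response. A lower response rate on SAIT101 would then appear as a positive unadjusted difference. In a biosimilarity report, two rows that disagree in direction, or a deficit shown as a gain, can mislead.

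The second fault is separate. Any pair of arms that does not include code 1 fails the condition for the adjusted CI, so one of the three comparisons named in the SAP would lack it.

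**Working it through.** The plan states no figure for this point, so there is none to reproduce. The code was traced and then applied to illustrative data.

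**Inputs.** From the SAP: column 1; event 1; first level minus second; CI only if a `level1` of 1 exists; alpha 0.05; 94 patients per arm. Assumed: responders 52/94, 42/94 and 47/94 in the arms coded 1, 2 and 3; a simulated baseline DAS28 as covariate; Rituxan coded 3.

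**(a) Direction.** For arms A and B,

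P(non-response in A) - P(non-response in B) = -[P(response in A) - P(response in B)].

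For codes 1 and 2: 42/94 - 52/94 = -10.6 points for non-response, and 52/94 - 42/94 = +10.6 points for response.

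The CI for a difference combines the two single-arm Wilson intervals. For 52/94 (55.32%) the interval is 45.26% to 64.96%. For 42/94 (44.68%) it is 35.04% to 54.74%. The distances from each estimate to its limits are 10.062 and 9.645 points, in mirrored order for the two arms. For response:

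- lower limit = 10.638 - √(10.062² + 10.062²) = 10.638 - 14.230 = -3.59
- upper limit = 10.638 + √(9.645² + 9.645²) = 10.638 + 13.640 = 24.28

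For non-response the limits are -24.28 and 3.59, the exact mirror.

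| Pair (codes) | Unadjusted as coded, 0/1 outcome | Adjusted | Unadjusted from responder column |
|---|---|---|---|
| 1 vs 2 | -10.6 (-24.28, 3.59) | +10.6 | +10.6 (-3.59, 24.28) |
| 1 vs 3 | -5.3 (-19.15, 8.80) | +5.5 | +5.3 (-8.80, 19.15) |
| 2 vs 3 | +5.3 (-8.80, 19.15) | -3.8 | -5.3 (-19.15, 8.80) |

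**Sensitivity to the outcome code.** If non-response is coded above 1 (for example response 1, non-response 2), column 1 is response. The code then prints +10.6 (-3.59, 24.28) beside +10.6, and there is no fault.

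**(b) Missing CI.** The number of estimate rows with `level1` equal to 1 is at least one for pairs (1, 2) and (1, 3), and zero for pair (2, 3). The last pair therefore goes to the branch that sets both limits to missing, and (-, -) is printed. Its adjusted point estimate comes from an earlier step and is still printed. If SAIT101 = 1 and MabThera = 2, the pair is MabThera-Rituxan. If the two codes are the other way round, it is SAIT101-Rituxan. This result does not depend on how response is coded.

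**The case against.** The strongest objection to (a) is that the code for non-response is not in the documents. Column 1 and event 1 agree if response is the lowest code, and neither the dataset specification nor the table shells are available. The shorter model statement in Appendix 5, "MODEL response (event='Y') = TRT base-DAS28-CRP", uses another dataset and variable, so it says nothing about `aval`. This stands: the reversal is likely, not proven. The explicit event option leans towards 0/1, because GENMOD by default models the lowest ordered value and the option would be redundant if that were 1. That is support only.

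Against (b), the treatment codes are borrowed from Appendix 4, and arms might be recoded before each call. The SAP history gives a plausible origin: the Appendix 5 code came in July 2018, and the MabThera-Rituxan comparison in January 2019. A fixed level 1 suits both SAIT101 pairs if SAIT101 is 1. Still, the printed macro does no recoding, so the dependence is real.

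The printed text is also not fully reliable. `&trtn` appears both as a variable name and as a list of values, so the code would not run as printed; this may come from the PDF conversion. Nor would either fault be well hidden. A missing CI is visible, and a reversed sign would contradict the per-arm proportions required by 15.2.3. The SAP history also records a dry run with sponsor comments. Ordinary program checking might catch both.

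A reader might infer that a similarity conclusion is at risk. The documents do not support that. No margin or decision rule attaches to these endpoints, and a mirrored CI has the same width and the same relation to zero.

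**Conclusion.** The point holds in a limited form.

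- **(a)** If `aval` is coded 0/1, the unadjusted differences and Wilson CIs for the binary secondary efficacy endpoints have reversed sign and mirrored limits. It would be too strong to call the reversal certain, since it disappears if non-response is coded above 1.
- **(b)** If Appendix 5 uses the Appendix 4 codes, exactly one pair has an adjusted estimate but no adjusted CI. It is MabThera-Rituxan if the codes follow the order of the call, and SAIT101-Rituxan if 1 and 2 are swapped. Both pairs are exploratory in 15.2.5.

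A reader might also infer that every categorical endpoint is affected at all five efficacy visits. That goes too far: major clinical response is defined only at Weeks 24 and 52, and EULAR response has three categories, so it is affected only if dichotomised. The reach is confined to secondary and exploratory categorical efficacy outputs. The PK co-primary endpoints and the DAS28 ANCOVA do not use this code. The planned methods are not in question, only their implementation. Correction before the final run is still worthwhile, because the SAP presents this as the code that will be used.

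**What to change.** 1. State the `aval` codes for response and non-response, and the three treatment codes, in Appendix 5.
2. Select the responder column explicitly. Either order the table so that response is column 1, keeping the treatment rows in their present order, or, under 0/1 coding, use COLUMN=2 and change the captured ODS OUTPUT table to RiskDiffCol2. COLUMN=2 alone is not enough, because the macro captures only the column-1 table. Under 1/2 coding, COLUMN=2 would create the reversal that it is meant to remove.
3. Replace both hard-coded uses of level 1, in the condition for computing the CI and in the selection of g, with the first treatment level of the current pair.
4. Check each unadjusted difference against the per-arm response proportions. Do not require sign agreement with the adjusted difference, since covariate adjustment can legitimately flip a sign when the arms are nearly equal.

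The cost is a few code edits and a short statement of codes. The design, the data and the planned analyses do not change.
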